# 4 Data Monitoring

An independent DSMC will monitor the progress of the trial and ensure that the safety of trial subjects is not compromised. The DSMC will review the clinical safety data prior to any individual dose titration and prior to initiation of subsequent age groups. The DSMC will review safety data and make an adjudication on: 1) the ability for any individual subject to escalate to the next higher dose and 2) the ability for enrollment to begin in the younger age groups (Groups 2 and 3). The DSMC consists of a clinical chair (pediatric cardiologist), and two physicians experienced in clinical trials with pediatric expertise (but not participating in this study). The DSMC Charter details the DSMC processes, duties, and responsibilities as well as the study-wide stopping criteria.

Data are provided to the DSMC as raw data listings for individual titration and age group reviews, as specified in the DSMC Charter. Additional summary analyses may be requested. For quarterly data reviews safety listings are provided to the DSMC. There is no separate Statistical Analysis Plan for the DSMC; the DSMC received as subset of the safety TFLs as required for the quarterly data reviews.

# 5 Statistical Methods

The statistical analyses will be reported using summary tables, listings, and figures (TLFs). Numbering for TLFs will be based on the recommended numbering convention provided by the International Conference on Harmonization (ICH).

The analyses described in this plan are considered *a priori*, in that they have been defined prior to database lock. Any analysis added after the database lock will be considered

exploratory. Post hoc analyses will be labeled as such on the output and identified in the CSR.

Unless noted otherwise, all statistical tests will be two-sided with a significance level of  $\alpha$  = 0.05 and descriptive in nature. Continuous variables will be summarized with means, standard deviations, medians, minimums, and maximums. Categorical variables will be summarized by counts and percent of subjects in corresponding categories. Missing values are not considered for percent calculations, unless stated otherwise. Footnotes may be used to specify the percent calculation as appropriate. Baseline for all analyses is defined in Section 5.2.3.

Individual subject data obtained via the electronic data capture (EDC) system and from external vendors (excluding PK data) will be presented in listings.

All analyses and tabulations will be performed using SAS version 9.4 or higher. Tables, listings, and figures will be presented in portable document format (PDF) and in Rich Text Format (RTF). All analyses will be subject to formal verification procedures. Specifically, results will be verified by independent programming. All documents will be reviewed by the lead statistician to ensure accuracy and consistency of analyses. The validation process will be used to confirm that statistically valid methods have been implemented and that all data manipulations and calculations are accurate. Checks will be made to ensure accuracy, consistency with this plan, consistency within tables and consistency between tables and corresponding data listings.

### 5.1 Determination of Sample Size

Sample sizes were estimated for this open-label study using within-subject change as the measure of improvement. Given the limited data from interventional trials in these patient populations and that this is the first clinical study of NNZ-2591 IMP in this population, treatment change estimates were based on Clinical Global Impression Scale of Improvement (CGI-I) data from completed clinical trials in other rare, neurodevelopmental disorders. Based on the information provided in Glaze et al. 2019 (Double-blind, randomized, placebo-controlled study of trofinetide in pediatric Rett syndrome), the standard deviation of the CGI-I is approximately 0.7 at a single timepoint. For a sample size of 10 subjects, a two-sided significance level of 0.05, and a Wilcoxon signed-rank test, the study will be able to detect a difference of 0.87 units of change in the CGI-I at a power of 0.90. For a power of 0.80, 0.85, and 0.90, the detectable difference would be 0.75, 0.80, and 0.87 or larger, respectively. The effect size for a power of 0.80, 0.85, and 0.90 is 1.07, 1.14, and 1.24, respectively. If the observed standard deviation is 1.5, the detectable difference for a power of 0.80, 0.85, and

0.90 is 1.61, 1.71, and 1.86 or larger, respectively. For a sample size of 20 subjects, a two-sided significance level of 0.05, and a Wilcoxon signed-rank test, the study will be able to detect a difference of 0.55 units of change in the CGI-I at a power of 0.90. For a power of 0.80, 0.85, and 0.90, the detectable difference would be 0.48, 0.51, and 0.55 or larger, respectively.

## 5.2 Handling of Data

### 5.2.1 Imputation of Missing/Incomplete Dates

An incomplete date is any date for which either the day, month or year is unknown, but all three fields are not unknown. An incomplete date occurs when the exact date an event occurred or ended cannot be obtained from a patient. For many of the analyses, a complete date is necessary to determine if the event should be included in the analysis (i.e., if the event is treatment-emergent or a medication is concomitant). In such cases, incomplete or missing dates will be imputed.

For incomplete or missing onset dates related to adverse events and concomitant medications, the dates will be imputed as follows:

- For an incomplete start date with missing day but month and year are present: If the reported month and year are the same as Day 1 month and year, then the date will be imputed as the date of Day 1. Otherwise, the start day will be imputed to the first day of the month.
- For an incomplete start date with missing day and month but year is present: If the reported year is the same as Day 1 year, then the date will be imputed as the date of Day 1. Otherwise, the start day will be imputed to January 1.
- If the reported date is completely missing, it will be imputed as the date of Day 1.

For concomitant medications, end dates will be imputed as follows:

- For an incomplete end date with missing day but month and year are present: The reported date will be imputed as the last day of the month.
- For an incomplete end date with missing day and month but year is present: If the reported year is the same as the study completion year, then the date will be imputed as the date of study completion. Otherwise, the end day will be imputed to December 31.
- If the date is completely missing, the event will be imputed as the date of study completion.

If any imputed date causes the end date to occur prior to the start date of the event, the start date of the event will be used for the imputation of the end date. If the imputed date is later than the date of study withdrawal, then the date of study withdrawal will be imputed for the date.

If the date of last dose is missing, then it will be imputed to the subject participation end date.

Dates related to efficacy measures will not be imputed.

In subject data listings, start and stop date of events will be displayed as reported on the eCRF (i.e., imputed values will not be listed).

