7. STUDY DESIGN

7.1 Study Design Overview

This is a Phase 2, open-label study of the safety and tolerability of NNZ-2591 Oral Solution, 50 mg/mL in male and female children and adolescents with Pitt-Hopkins syndrome. Approximately 10 to 20 male and female participants between the ages of 3 and 17 years will be enrolled and receive treatment of NNZ-2591 Oral Solution, 50 mg/mL for a total of 13 weeks. Additional participants may be screened, enrolled, and treated to achieve approximately 20 study completers.

There will be a total of 17 study visits, comprising 5 in-clinic visits, and 12 remote telemedicine/in-home nurse visits. The study will commence with an approximately 4 to 6 week Screening and Baseline period. During this Screening/Baseline period, participants will be assessed for study eligibility and data will be collected to establish the participant's baseline characteristics and symptom severity using a variety of assessments (Section 9.2). Two in-clinic visits and one remote/in-home visit (Visits 1, 2, 3) comprise Screening and Baseline.

Once eligibility is confirmed, participants will receive the starting dose of 4 mg/kg and then be up-titrated to the target dose (see Section 7.2). Participants will receive treatment for a total of 13 weeks. During the treatment period, there are three in-clinic visits: Week 2 (Visit 5), Week 6 (Visit 9) and Week 13 (Visit 16). There is a combined remote, telemedicine visit by the site investigator and an in-home visit by a visiting nurse for safety at Week 1 (Visit 4), Week 4 (Visit 7), Week 8 (Visit 11) and Week 10 (Visit 13). These combination remote/in-home visits will be conducted simultaneously whenever possible, or they will be conducted on the same day with the telemedicine visit occurring first. If it is not feasible to conduct these visits simultaneously or on the same day, the telemedicine portion of the visit and the nurse portion of the visit must be conducted on two consecutive days. In-home visits with a visiting nurse will be done at Weeks 3 (Visit 6), 5 (Visit 8), 7 (Visit 10), 9 (Visit 12), 11 (Visit 14), and 12 (Visit 15).

All participants will also have a remote post-treatment visit with the Investigator via telemedicine and an in-person home visit by a visiting nurse approximately 2 weeks after the end of treatment (Week 15, Visit 17).

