7.4 Study Timeline

The study duration is 19 weeks from Screening to Follow-Up at Week 15 (+4 days).

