9.4.2 Investigational Medicinal Product Administration

NNZ-2591 Oral Solution, 50 mg/mL will be administered open-label at a target dose of 12 mg/kg BID. The total administration period for NNZ-2591 will be 13 weeks. Participants will be up-titrated to the target dose according to the dosing schedule outlined in Section 7.2. The dose titration schedule may be modified based on updated PK modelling including data from the study.

NNZ-2591 Oral Solution, 50 mg/mL, is provided as a ready-to-use strawberry-flavored liquid for oral administration. The IMP should not be mixed with water, liquid thickeners, or food for administration.

Each day there will be two dose administrations, one in morning and one in afternoon or evening. There should be at least 8 hours between doses. Doses should be given on an empty stomach (2 hours after the previous meal or snack and 30 minutes prior to the next). Doses may be taken over a 10-minute period with a follow up of 250 mL of water.

For all participants, the total duration of NNZ-2591 treatment will be 91 days. Dosing at the end of Baseline counts as Day 1 whether one or two doses are given. Dosing may not exceed 91 days including Day 1, and all efficacy assessments for the EOT visit must be completed on or before Day 91 of treatment.

The first dose of IMP will be administered in the clinic after all Baseline assessments are completed or, if the Investigator judges that it is too late in the day, on the following day. The participant should be monitored for at least three hours after the first dose. If the first dose is administered the day following Baseline, vital signs (except height) should be collected before the dose is administered. Day 1 of dosing is defined by the date when the first dose is taken. At this visit, the site will provide IMP for the caregiver to dispense at home. Enough IMP will be provided to cover the interval until the next in-clinic visit when the caregiver will be re-supplied from site.

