### 5.3 Definitions

- Age will be derived as the integer value of (informed consent/assent date date of birth + 1)/365.25.
- The age at time of assessment will be derived as the integer value of (date of assessment date of birth + 1)/365.25.

- Body Mass Index (BMI) will be derived as weight in kilograms divided by height in meters squared.
- The change from Baseline measurement for a variable at a particular visit will be derived as the measurement taken at the specified visit minus the baseline measurement. For the Clinical Global Impression Scale Improvement and Caregiver Impression of Change, change from Baseline is the value at the visit.
- Treatment duration in days will be derived as follows: Date of Last Dose Date of First Dose + 1.
- The number of expected doses will be derived as (2\*treatment duration in days)-1, as subjects are expected to receive only their morning dose on the last day of treatment
- The number of doses taken will be derived as the number of doses taken as indicated by the Administration of First Dose CRF and by the Daily Dosing Log CRF for remaining doses, based on completed date and dose fields
- Number of missed doses will be derived based on the number of expected doses the number of doses taken
- Study Day will be derived as Date of Event Date of First Dose (+1 if the date of event ≥ date of first dose)
- Screening/baseline duration in days will be derived as follows: Date of First Dose Date of Screening
- Study duration will be defined as the total number of days in the study (date of last visit date of informed consent + 1).
- History of developmental regression will be determined from the PTHS diagnosis page of the CRF question: "Has the child undergone a regression of skills in the past?" If coded as "yes" the subject is considered as having had a past developmental regression.
- Autism Spectrum Disorder (ASD) diagnosis will be derived from the PTHS diagnosis page of the CRF. If ASD is checked under "confirmation of psychiatric co-morbidities", the subject is considered as having the disorder.
- Bipolar Disorder will be derived from the PTHS diagnosis page of the CRF. If "Bipolar disorders" is checked under "confirmation of psychiatric comorbidities", the subject is considered as having the disorder.

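### A missing last-dose date is set to the end of study participation, which for a child who reaches Visit 17 is 14 to 19 days past the dosing limit and inflates treatment duration and missed doses

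*SAP*

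**What the plan says.** SAP Section 5.2.1 gives one rule for this date: "If the date of last dose is missing, then it will be imputed to the subject participation end date". The only cap in that section is study withdrawal: "If the imputed date is later than the date of study withdrawal, then the date of study withdrawal will be imputed for the date". Neither the SAP nor its addendum defines the participation end date.

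Protocol Section 9.4.2 says that "the total duration of NNZ-2591 treatment will be 91 days" and that "Dosing may not exceed 91 days including Day 1". The end-of-treatment (EOT) visit is held while the child is still on drug (Protocol Table 1, footnote b). Visit 17 follows about two weeks later, at Week 15 with a +4-day window (Protocol Sections 7.1 and 7.4).

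SAP Section 5.3 computes treatment duration as the last-dose date minus the first-dose date plus 1, expected doses as twice that duration minus 1, and missed doses as expected minus taken. Doses taken are counted from the first-dose form and the Daily Dosing Log. The addendum adds only that a negative count of missed doses becomes 0. SAP Section 7.1 summarizes treatment duration and missed doses, and confines missed doses to the time before treatment is discontinued.

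**The concern.** The study has an off-drug follow-up, so the end of participation and the end of dosing are different dates by design. Using the first for the second adds off-drug days to treatment duration. Doses taken come from dated records and do not rise to match, so each added day counts as two missed doses.

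Safety and tolerability are the primary objective, and SAP Section 7 names dosing compliance as a tolerability measure. Treatment duration is also the denominator of the on-treatment monthly rate of major breathing episodes (SAP Section 5.3), which SAP Section 7.10 compares with baseline by a Wilcoxon signed rank test. The numerator covers Visits 4 to 16. A denominator running to Visit 17 therefore lowers the rate with no change in the child, and the shift favors the drug.

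The protocol does not rescue the rule, because SAP Section 2 says the SAP governs where the two disagree on planned analyses.

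**Working it through.** **Inputs**

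- Dosing limit: 91 days including Day 1 (Protocol Section 9.4.2).
- Visit 17: Week 15, +4 days (Protocol Sections 7.1 and 7.4). 15 × 7 = 105, so the nominal day is 105 or 106 depending on how the days are numbered. With the window, the latest is 106 + 4 = Day 110.
- Expected doses = 2 × duration − 1 (SAP Section 5.3).
- Planned enrollment: 10 to 20 (SAP Section 2.2).
- Assumptions for the completer: true last dose on Day 91, all doses taken, two doses on Day 1, participation ending at Visit 17.

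**The plan's own figure.** 13 weeks × 7 = 91 days. Expected doses are 2 × 91 − 1 = 181, and missed doses are 181 − 181 = 0. The formulas are coherent when the last-dose date is right.

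**The same child with the last-dose date missing**

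| Quantity | True date | Imputed, Day 105 | Imputed, Day 110 |
|---|---|---|---|
| Treatment duration (days) | 91 | 105 (+14, +15.4%) | 110 (+19, +20.9%) |
| Expected doses | 181 | 2 × 105 − 1 = 209 | 2 × 110 − 1 = 219 |
| False missed doses | 0 | 209 − 181 = 28 | 219 − 181 = 38 |
| Doses taken / expected | 100% | 181/209 = 86.6% | 181/219 = 82.6% |
| Multiplier on breathing-episode rate | 1 | 91/105 = 0.867 | 91/110 = 0.827 |

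The addendum's floor at 0 does nothing here, because the error is positive. If only one dose is given on Day 1, the child has 180 doses taken and one missed dose even with the true date. The excess of 28 to 38 is unchanged.

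**Effect on a group mean.** One such child shifts mean duration by 14/20 = 0.7 to 19/10 = 1.9 days, and mean missed doses by 28/20 = 1.4 to 38/10 = 3.8.

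**Early stopper who stays on study.** Protocol Sections 9.4.2 and 9.4.5 allow a child to stop drug without withdrawing. Take a last dose on Day 22, as an assumption, with participation to Visit 17. The overshoot is 105 − 22 = 83 to 110 − 22 = 88 days. Two doses a day gives 166 to 176 false missed doses, unless the limit in SAP Section 7.1 is somehow applied.

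**Child who leaves at or near the last dose.** The error is the gap between last dose and exit: none on the same day, and 7 days and 14 false missed doses for a one-week gap.

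**The case against.** **The rule may seldom or never be used.** Dosing is recorded daily, the log is reviewed at every post-baseline visit through EOT, returned drug is reconciled, and omissions on the case report form must be explained. Nothing in the documents shows that any last-dose date is missing. This stands: the figures above are per affected child, not a forecast for the trial. The documents also do not say where the last-dose date comes from. If it already comes from the Daily Dosing Log, the rule acts only when the log has no usable date.

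**The participation end date need not be Visit 17.** A child who stops after Visit 5 is to return for EOT assessments and complete the exit form. If that exit ends participation, the error is only the gap since the last dose. This also stands. A reader might infer that the imputed date can never be a dosing date, but that is too strong.

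**SAP Section 7.1 already limits missed doses.** It shows that off-drug days were not meant to count. But it supplies no stop date when the last-dose date is missing, and the Section 5.3 formula would still use the imputed duration. The limit is evidence of a conflict and does not remove it.

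**The reach is limited.** Treatment-emergent events are defined from the first dose, so overall incidence does not depend on this date. No cumulative-dose summary is planned, the tests are described as descriptive, and medians would move less than means. All of this stands.

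A reader might also infer that missing dates cluster in children who stopped early, so that the error falls on those most informative about tolerability. That is plausible, but neither document supports it, and Protocol Section 8.4 requires the reason for discontinuation to be recorded and the sponsor notified.

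**Conclusion.** The rule is wrong as written, but conditional. If it is triggered for a child who reaches Visit 17, it puts the last dose in a period when dosing has ended. A fully adherent completer then gains 14 to 19 days of treatment duration and 28 to 38 false missed doses, and the breathing-episode rate is multiplied by about 0.83 to 0.87. These figures assume a true last dose on Day 91 and participation ending at Visit 17. The error is larger for an early stopper kept on study and can vanish for a child who leaves with the last dose.

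How much the reported results would change depends on how many last-dose dates are missing, which the documents do not give. They do not support a claim that the trial's exposure summary is in fact inflated. They do support correcting the rule, since it conflicts with the protocol's dosing limit and with SAP Section 7.1, and the SAP already relies on a better source for the date.

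**What to change.** Replace the sentence in SAP Section 5.2.1 with this rule:

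- Impute a missing last-dose date to the last dated dose in the Daily Dosing Log.
- Only if the log has no usable date, use the earliest of the recorded treatment-discontinuation date, the EOT or early-termination visit date, and Day 91.
- Do not truncate dosing that the log shows after Day 91. That would be a protocol deviation and should remain visible.

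Define the participation end date, and state in Section 7.1 that missed doses are counted to the same stop date as treatment duration. With a log date of Day 91, the completer above returns to 91 days, 181 expected doses and no missed doses.

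The cost is a few sentences in the SAP or its addendum and a small programming change, with no new data. Under SAP Section 5 it must be in place before database lock to count as prespecified. Reporting the number of imputed last-dose dates would show whether the point mattered.

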### 5.2.2 Imputation of Alphanumeric Data

Should there be instances where a clinical laboratory parameter is reported with embedded non-numeric characters, for example, "<0.1" or ">10", the data will be imputed for quantitative summaries. The actual values as reported in the database will be presented in data listings.

For incorporation in quantitative summaries, the following imputation rule will be employed:

- For values reported as less than a lower limit of detection, the value will be imputed as half of the numeric result preceded by the '<' symbol. For example, "<0.1" will be imputed to 0.05.
- For values reported as greater than an upper limit of detection, the value will be imputed as the numeric result preceded by the '>' symbol. For example, ">10" will be imputed as 10.

### 5.2.3 Visit Windows

Unscheduled assessments that occur on the same day as a scheduled visit will be considered with the corresponding scheduled visit for analysis. Otherwise, unscheduled assessments will be considered with the most recently completed scheduled visit for analysis. If multiple assessments are windowed to the same visit for analysis, the results from the latest assessment will be used, as repeats may have been done to confirm abnormalities, per the protocol. Any unscheduled visits occurring during the Screening period will not be mapped to a scheduled visit but will be considered in the derivation of the Baseline value.

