### 5.2.4 Baseline Values

Baseline values that are missing will not be imputed for safety or efficacy measures. For efficacy assessments scheduled to be collected at more than one visit during the Screening/Baseline period, the baseline value will be based on the average of all nonmissing values from assessments conducted prior to the first dose of study drug. For assessments scheduled to be collected once during the Screening/Baseline period, the value from the most recent non-missing assessment prior to the first dose will be used. For safety and other assessments, the value from the most recent non-missing assessment prior to the first dose will be used.

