## 7.3 Clinical Laboratory Evaluations

Blood will be collected at Visit 1 (Screening), Visit 3 (Week 0), and Visit 13 (End of Treatment). Urine samples will be collected at all visits. Laboratory parameters (chemistry, hematology, urinalysis) will be presented in data listings. Abnormal values will be flagged as high or low relative to normal ranges, where applicable, by the laboratory vendor.

Change from baseline in quantitative laboratory parameter values will be summarized using descriptive statistics at all visits.

For those laboratory tests in which normal ranges are available, shifts from baseline will be presented. Categories for the shift tables will be high, normal, and low.

Laboratory parameters will be classified according to the categories given by the laboratory vendor. The laboratory parameters from the vendor listed below will be assigned to the following categories for data summaries.

Chemistry	Hematology	Urinalysis
Bun/Creatinine Ratio	PT/INR/APTT	Microalbumin, UR
EGFR (Bedside Schwartz)		Random
Hemoglobin A1C		Urine Chemistry
Pregnancy, qualitative		
Thyroxine, Free		
Triiodothyronine, Free		
TSH Ultrasensitive		
Urine Drug Screen w/ Con		

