### 7.6 Vital Signs

Weight, blood pressure (systolic and diastolic in mmHg), heart rate (bpm), respiratory rate (rpm), and body temperature (°C) will be collected at the Screening visits (Visit 1 and 2) and all post-baseline study visits. Ideally, vital signs will be taken after the subject has been seated for 5 minutes. The initial blood pressure reading will be summarized in the table. Height will be taken at the Screening visit (Visit 1), Visit 3 (Week 0), and End of Treatment (Week 13, Visit 16).

Summary statistics for each measurement and the change from baseline will be presented at each post-baseline visit. All vital sign measurements will be presented in data listings. A separate table and listing will be provided for blood pressure.

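### SAP 5.2.3 keeps the latest result assigned to a visit, so the laboratory and ECG tables tend to lose unconfirmed abnormal values, and a post-dose recheck can replace the on-treatment EOT value

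*SAP*

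**What the plan says.** SAP 5.2.3 sets two rules. An unscheduled assessment on the day of a scheduled visit goes with that visit; for other days, "unscheduled assessments will be considered with the most recently completed scheduled visit for analysis". If a visit then holds more than one result, "the results from the latest assessment will be used, as repeats may have been done to confirm abnormalities".

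SAP 7.3 plans by-visit change from baseline for quantitative laboratory parameters. It adds that "For those laboratory tests in which normal ranges are available, shifts from baseline will be presented", in the categories high, normal and low. SAP 7.7 plans the same summaries for ECG parameters, and shifts in ECG interpretation at each post-baseline visit. Neither section has its own rule for repeats, so 5.2.3 governs both. Neither mentions a worst post-baseline value.

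Blood pressure is treated differently. SAP 7.6 states that "The initial blood pressure reading will be summarized in the table". The safety baseline is the last pre-dose result (SAP 5.2.4: "For safety and other assessments, the value from the most recent non-missing assessment prior to the first dose will be used").

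**The concern.** Safety and tolerability are part of the primary objective. If repeats follow abnormal results more often than normal ones, keeping the latest value acts mainly on the abnormal ones. A high that is not confirmed disappears from the table, while a normal scheduled value usually has no repeat to displace it. The tables then drift towards normal even when a first value was a genuine transient effect.

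The mapping rule adds a separate problem. The EOT visit takes place while the participant is still on drug (Protocol, footnote b to Table 1). An unscheduled recheck after the last dose and before Visit 17 belongs, under 5.2.3, to the EOT visit and replaces its value. The table would then show an off-drug result as an on-treatment one.

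**Working it through.** **Do repeats depend on the result?** The SAP's own reason for the rule says that they may. The protocol agrees:
- Section 8.3 allows resampling of out-of-range screening results.
- Section 9.5.2 allows additional tests when results are abnormal.
- Sections 9.4.5 and 9.5.8 call for a repeat ECG to confirm QTcF prolongation.
- Section 9.1 allows unscheduled nurse visits for repeat laboratory tests.

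Other triggers also exist. Section 9.5.8 has technically poor ECGs retaken, and Section 10.8.3 allows extra tests to investigate an AE. The selection is a tendency and not absolute.

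**Size under a simple model.** The plan gives no figure to reproduce. The inputs below are assumptions, not document values:
- The scheduled and repeat values are bivariate normal with correlation r.
- The upper limit is at z = 1.96 (97.5th percentile).
- The drug shifts the mean by s SD.
- A fraction q of highs is repeated, and normal values are not repeated.

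The formulas are:
- P(high, scheduled): p = 1 − Φ(1.96 − s)
- P(high on both): b, the bivariate normal upper tail beyond 1.96 − s in both values
- P(high, reported) = (1 − q)·p + q·b

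For s = 0.5, p = 1 − Φ(1.46) = 7.21%. With r = 0.7, b = 3.10%, so:
- q = 0.2: 0.8 × 7.21 + 0.2 × 3.10 = 6.4%
- q = 0.5: 0.5 × 7.21 + 0.5 × 3.10 = 5.2%
- q = 1: 3.1%

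The same formula over a wider range:

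| s (SD) | r | Scheduled high | Reported, q = 0.2 | q = 0.5 | q = 1 |
|---|---|---|---|---|---|
| 0 | 0.5 | 2.5% | 2.1% | 1.5% | 0.5% |
| 0 | 0.7 | 2.5% | 2.2% | 1.7% | 0.8% |
| 0 | 0.9 | 2.5% | 2.3% | 2.0% | 1.5% |
| 0.5 | 0.5 | 7.2% | 6.2% | 4.6% | 2.0% |
| 0.5 | 0.7 | 7.2% | 6.4% | 5.2% | 3.1% |
| 0.5 | 0.9 | 7.2% | 6.7% | 6.0% | 4.8% |
| 1 | 0.5 | 16.9% | 14.8% | 11.8% | 6.8% |
| 1 | 0.7 | 16.9% | 15.3% | 13.0% | 9.1% |
| 1 | 0.9 | 16.9% | 16.0% | 14.6% | 12.4% |

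With 20 participants (the top of the planned 10 to 20), s = 0.5 and r = 0.7, the expected highs per parameter and visit are 20 × 7.21% = 1.44 from scheduled values. Under the latest-value rule they are 1.03 (q = 0.5) or 0.62 (q = 1). With s = 1 and r = 0.7 they are 3.37, against 2.59 or 1.81.

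The direction is the same in every row because the model repeats only highs. If repeats were unrelated to the result, there would be no systematic drift.

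**What a worst-value table would do.** The metabolic panel is taken at every visit except Visit 2, so there are 13 scheduled on-treatment panels (Visits 4 to 16). For an inert parameter with equal correlation r between visits,

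P(any of 13 high) = 1 − ∫ φ(u) · Φ((1.96 − √r·u)/√(1 − r))^13 du.

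This gives 17% at r = 0.5, 12% at r = 0.7 and 7% at r = 0.9, against 2.5% at a single visit.

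**The case against.** The strongest case on the other side has four parts.

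- **The rule works in both directions.** A test prompted by symptoms that comes back abnormal maps to the last completed visit and can replace a normal value. A worsening repeat replaces a milder one. This stands. A reader might infer that only abnormal values are ever repeated and that normal values are never lost; the documents do not support that.
- **Safety conclusions do not rest on these tables alone.** AE and SAE incidence is untouched by the rule. Clinically significant laboratory and ECG findings become AEs if they meet the definition (Protocol 10.5). The listings keep the values, and the DSMC decides titration and age-group steps from raw listings (SAP 4). This also stands, so a reader should not infer that the rule affects all safety summaries or the DSMC's titration and age-group decisions.
- **Much of the detail is not visible.** SAP 7.3 does not say whether laboratory shifts are by visit, last or worst, and the table list is kept outside the SAP. The follow-up plans cited as Protocol 9.5.2.1 to 9.5.2.3 are not in the public text. The frequency of repeats and of off-drug rechecks therefore cannot be judged. The metabolic panel is also scheduled weekly in treatment, so most mapping gaps for it are short.
- **Removing unconfirmed values may remove noise.** The protocol itself asks for a confirming ECG before acting on QTcF. That is a fair reason to show the repeat, but not to drop the first value from every table.

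The blood pressure exception is weak evidence of inconsistency. Protocol 9.5.1 provides for repeat readings within a visit, and SAP 7.6 most naturally chooses among those.

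**Conclusion.** The concern holds as a tendency. As written, SAP 5.2.3 favours later values over unconfirmed abnormal ones in the by-visit laboratory and ECG tables and in the ECG shifts. The laboratory shifts are affected too if they are built from the same visit values. The rule also allows a result taken after the last dose to stand as the EOT value. The second point follows from the wording alone and needs no model.

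The size of the drift is not known. It may be tempting to quote the fall from 7.2% to 3.1% as the expected effect, but that assumes every high is repeated. The protocol leaves additional tests to judgement, and at lower repeat rates the fall is to 5.2% (half repeated) or 6.4% (a fifth repeated). All three figures also assume s = 0.5 SD and r = 0.7.

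The point is worth correcting because safety is a primary objective, the groups are small and the change is cheap. It does not put the AE analysis in doubt.

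**What to change.** In SAP 5.2.3, for laboratory and ECG data:
1. Use the scheduled assessment in by-visit summaries and by-visit shifts. Use a repeat only where the scheduled result is missing or technically invalid.
2. Do not let a result obtained after the last dose count towards an on-treatment visit. Show it separately as post-treatment.
3. Add a supplementary shift from baseline to the worst on-treatment value, including unscheduled and repeat results, and state in SAP 7.3 and 7.7 which format each shift table has.

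The cost is SAP wording, one derived flag and one extra table per domain. No new data are needed and trial conduct does not change. The downside should be stated in the table's footnote. A worst value over 13 metabolic-panel visits flags about 7% to 17% of participants on an inert parameter (r = 0.9 to 0.5, with the limit at the 97.5th percentile), and there is no control arm to calibrate against. The worst-value table should therefore sit beside the by-visit tables and not replace them.
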